9.2. Appendix B Standards for Variable Display in Tables, Figures and Listings (TLFs)

Continuous Variables: The precision for continuous variables will be based on the precision of the data itself. The mean and median will be presented to one decimal place more than the original results; the SD will be presented to two decimal places more than the original results; and the minimum and maximum will be presented to the same precision as the original results.

Categorical Variables: Percentages will be presented to one decimal place unless otherwise stated.

9.3. Analysis Visit Windows for Immunogenicity Analysis

Immunogenicity Analysis will be summarized using the following analysis visit window for post-injection assessments:

Step 1: If the immunogenicity assessments are collected at a scheduled visit, the collected data will be mapped to the nominal scheduled visit and the data collected at scheduled visit will be used.

Step 2: If the immunogenicity assessments are not collected at the scheduled visit, any assessments collected at unscheduled visits will be used using the analysis visit windows described in Table 7 below.

If a participant has multiple assessments within the same analysis visit, the following rule will be used:

- If multiple assessments occur within a given analysis visit, the assessment closest to the target study day will be used.
- If there are 2 or more assessments at equal distance to the target study day, the last assessment will be used.

Table 7: Analysis Visit Windowing

| Visit | Target Study Day | Visit Window in Study Day |
|-----------------------|-----------------------|---------------------------|
| Immunogenicity | | |
| Day 1 | 1 (Date of Injection) | 1, Pre-vaccination |
| Day 29 | 29 | [2, 105] |

9.4. Appendix C Imputation Rules for Missing Dates of Prior/Concomitant Medications

Imputation rules for missing or partially missing start/stop dates are defined below:

1. Missing or partially missing medication start date

- If only day is missing, use the first day of the month, unless the start month and year of the medication coincide with the start month and year of the IP injection :
 - If not marked as a prior medication on the Prior/Concomitant CRF page (“Was the medication taken prior to study administration?” = “No”), then use the date of IP injection.
 - If marked as a prior medication on the Prior/Concomitant CRF page (“Was the medication taken prior to study administration?” = “Yes”), then use the earlier of the first day of the month or the date of IP injection - 1.
 - If the mark on the Prior/Concomitant CRF page (“Was the medication taken prior to study administration?”) is missing and the medication end date is on/after the date of IP injection or is missing, then use the date of IP injection.
- If day and month are both missing, use the first day of the year, unless the start year of the medication coincide with the start year of the IP injection :
 - If not marked as a prior medication on the Prior/Concomitant CRF page (“Was the medication taken prior to study administration?” = “No”), then use the date of IP injection.

- If marked as a prior medication on the Prior/Concomitant CRF page (“Was the medication taken prior to study administration?” = “Yes”), then use the earlier of the first day of the year or the date of IP injection -1.
- If the mark on the Prior/Concomitant CRF page (“Was the medication taken prior to study administration?”) is missing and the medication end date is on/after the date of IP injection or is missing, then use the date of IP injection.
- If day, month, and year are all missing, the date will not be imputed, but will use the following rules for purposes of determining the status as prior and/or concomitant.
 - If not marked as a prior medication on the Prior/Concomitant CRF page (“Was the medication taken prior to study administration?” = “No”), then the medication will be treated as having begun after IP injection;
 - If marked as a prior medication on the Prior/Concomitant CRF page (“Was the medication taken prior to study administration?” = “Yes”), or if the mark is missing, then the medication will be treated as a prior medication (and as a concomitant medication unless the stop date indicates the medication was stopped prior to IP injection).

2. Missing or partially missing medication stop date:

- If only day is missing, use the last day of the month, study completion or discontinuation from the study, or death, whichever is the earliest.
- If day and month are both missing, use the last day of the year, study completion or discontinuation from the study, or death, whichever is the earliest.
- If day, month, and year are all missing, the date will not be imputed, but the medication will be flagged as a continuing medication (i.e., concomitant).

In summary, the prior and concomitant categorization of a medication is described in the table below.

Table 8: Prior and Concomitant Categorization of Medications and Non-Study Vaccinations

| Medication Start Date | Medication End Date | |
|--|----------------------------------|--|
| | < Injection Date of IP | ≥ Injection Date and ≤ Injection 28 Days After Injection[1] |
| < Injection date of IP [2] | P | P, C |
| ≥ Injection date and ≤ 28 days after injection | - | C |
| > 28 days after injection | - | - |

P = Prior; C = Concomitant

[1] includes medications with completely missing end date

[2] includes medications with completely missing start date, unless marked as not administered as a prior medication on the Prior/Concomitant CRF page (“Was the medication taken prior to study administration?”=“No”)

9.5. Appendix D Imputation Rules for Missing Dates of AEs

Imputation rules for missing or partial start dates and stop dates of AEs are defined below:

1. Missing or partially missing start date:

- If only day is missing, use the first day of the month, unless:
 - The AE end date is on/after the date of IP injection or is missing/partial AND the start month and year of the AE coincide with the start month and year of the IP injection. In this case, use the date of IP injection.
- If day and month are both missing, use the first day of the year, unless:
 - The AE end date is on/after the date of IP injection or is missing/partial AND the start year of the AE coincides with the start year of the IP injection. In this case, use the date of IP injection.
- If day, month, and year are all missing, the date will not be imputed. However, if the AE end date is prior to the date of IP injection, then the AE will be considered a pre-treatment AE. Otherwise, the AE will be considered treatment-emergent.

2. Missing or partially missing end dates will not be imputed.

9.6. Appendix E Estimands and Estimand Specifications**Table 9: Intercurrent Event Types**

| Label | Intercurrent Event Type | Comment |
|---|---|--|
| IcEv1 (early discontinuation or death without confirmation of cases, i.e., unrelated death) | Unrelated death without documented influenza | Participants in PP Set who withdraw consent or die due to reasons unrelated to influenza will be included in primary efficacy analysis. |
| IcEv2 (early infection) | Infection starting up to 14 days after the study intervention | Participants in PP Set who experience an early influenza infection up to 14 days after the IP will be included in primary efficacy analysis. |
| Abbreviation: IcEv: intercurrent event, PP: per-protocol. | | |

Table 10: Primary Objective and Estimands with Rationale for Strategies to Address Intercurrent Events for Per-Protocol Analysis

| Objective: To demonstrate the efficacy of mRNA-1010 to prevent influenza | |
|---|--|
| Estimand Description | rVE will be measured using 1 – HR (mRNA-1010/ Fluarix) from 14 days after study intervention. A hypothetical strategy will be used for early discontinuation (e.g., withdrawal consent, deaths unrelated to influenza) or early infection in participants in the PP Set. |
| Target Population | Adults aged 50 years and older |
| Variable/Endpoint | 
Time-to-first episode of RT-PCR confirmed protocol-defined ILI:
 
 • For participants who experience at least one RT-PCR confirmed protocol-defined ILI, this will be the number of days from the date of randomization to the earliest start date of RT-PCR confirmed protocol-defined ILI. If the earliest start date is < 14 days following randomization, the value will be censored. • For participants who do not experience RT-PCR confirmed protocol-defined ILI, this will be the number of days from the date of randomization to the earliest date of: 
 ○ early discontinuation or death unrelated to influenza ○ Day 181/Month 6 or the end of the influenza season (whichever occurs later). 
All values for or participants who do not experience RT-PCR confirmed protocol-defined ILI will be censored.
 |
| Treatment Condition(s) | Test: mRNA-1010 Reference: Active Comparator (Fluarix®) |
| Estimand Label | Estimand 1 |
| Population-Level Summary | rVE defined as 1 - HR of mRNA-1010/active comparator |

| | |
|--|--|
| Intercurrent Event Strategy | |
| IcEv1 (Early discontinuation or unrelated death): | Hypothetical |
| IcEv2 (Early infection): | Hypothetical |
| Rationale for Strategy(s) | Hypothetical: early discontinuation (including unrelated death) censored at time of discontinuation (or at time of death), and early case will be censored at the time of initial onset, handled with independent censoring. |

9.7. Appendix F Solicited Adverse Reactions and Grades

Table 11: Solicited Adverse Reactions and Grades

| Reaction | Grade 1 | Grade 2 | Grade 3 | Grade 4¹ |
|---|-------------------------------|---------------------------------|-------------------------|--|
| Injection site pain | No interference with activity | Some interference with activity | Prevents daily activity | Emergency room (ER) visit or hospitalization |
| Injection site erythema (redness) | 25 - 50 mm/ 2.5 - 5 cm | 51 - 100 mm/ 5.1 - 10 cm | > 100 mm/ > 10 cm | Necrosis or exfoliative dermatitis |
| Injection site swelling/induration (hardness) | 25 - 50 mm/ 2.5 - 5 cm | 51 - 100 mm/ 5.1 - 10 cm | > 100 mm/ > 10 cm | Necrosis |
| Axillary (underarm) swelling or tenderness ipsilateral to the side of injection* | No interference with activity | Some interference with activity | Prevents daily activity | ER visit or hospitalization |
| Headache | No interference with activity | Some interference with activity | Prevents daily activity | ER visit or hospitalization |
| Fatigue | No interference with activity | Some interference with activity | Prevents daily activity | ER visit or hospitalization |
| Myalgia (muscle aches all over body) | No interference with activity | Some interference with activity | Prevents daily activity | ER visit or hospitalization |

| Reaction | Grade 1 | Grade 2 | Grade 3 | Grade 4¹ |
|---|---|--|---|---|
| Arthralgia (joint aches in several joints) | No interference with activity | Some interference with activity | Prevents daily activity | ER visit or hospitalization |
| Nausea/vomiting | No interference with activity or 1-2 episodes/ 24 hours | Some interference with activity or > 2 episodes/ 24 hours | Prevents daily activity, requires outpatient IV hydration | ER visit or hospitalization for hypotensive shock |
| Chills | No interference with activity | Some interference with activity not requiring medical intervention | Prevents daily activity and requires medical intervention | ER visit or hospitalization |
| Fever (oral) | 38.0 – 38.4°C 100.4 – 101.1°F | 38.5 – 38.9°C 101.2 – 102.0°F | 39.0 – 40.0°C 102.1 – 104.0°F | > 40.0°C > 104.0°F |

Abbreviation: ER = Emergency room.

Note: Events listed above but starting > 7 days post study injection will be recorded on the AE page of the eCRF. Causality for each event reported on the AE page will be determined per assessment by the Investigator.

¹ Grading of Grade 4 events will be determined per Investigator and assessment is recorded on the reactogenicity event page in the electronic case report form.

Source: Guidance for Industry – Toxicity Grading Scale for Healthy Adult and Adolescent Volunteers Enrolled in Preventive Vaccine Clinical Trials ([DHHS2007](#)).

9.8. Appendix G Adverse Events of Special Interest Terms**Table 12: Adverse Events of Special Interest**

| Medical Concept | Additional Notes |
|---|--|
| Thrombocytopenia | 
 • Platelet counts < 150 × 10⁹ • Including but not limited to immune thrombocytopenia, platelet production decreased, thrombocytopenia, thrombocytopenic purpura, thrombotic thrombocytopenic purpura, or HELLP syndrome |
| New onset of or worsening of the following neurologic diseases: | 
 • Guillain-Barre Syndrome • Acute disseminated encephalomyelitis • Idiopathic peripheral facial nerve palsy (Bell's palsy) • Seizures including but not limited to febrile seizures and/or generalized seizures/convulsions |
| Anaphylaxis | 
 • Anaphylaxis as defined per protocol (Section Error! Reference source not found.) • Follow reporting procedures in the protocol (Section Error! Reference source not found.) |
| Myocarditis/Pericarditis | 
 • Myocarditis • Pericarditis • Myopericarditis |

Abbreviation: HELLP = hemolysis, elevated liver enzymes, and low platelet count.

9.9. Appendix H Severity Grading of Vital Sign Abnormalities**Table 13: Severity Grading of Vital Sign Abnormalities**

| Vital Signs* | Mild (Grade 1) | Moderate (Grade 2) | Severe (Grade 3) | Potentially Life Threatening (Grade 4) |
|---------------------------------------|------------------------------|------------------------------|--------------------------|--|
| Fever (°C)** (°F)** | 38.0 – 38.4 100.4 – 101.1 | 38.5 – 38.9 101.2 – 102.0 | 39.0 – 40 102.1 – 104 | > 40 > 104 |
| Tachycardia - beats per minute | 101 – 115 | 116 – 130 | > 130 | ER visit or hospitalization for arrhythmia |
| Bradycardia - beats per minute*** | 50 – 54 | 45 – 49 | < 45 | ER visit or hospitalization for arrhythmia |
| Hypertension (systolic) - mm Hg | 141 – 150 | 151 – 155 | > 155 | ER visit or hospitalization for malignant hypertension |
| Hypertension (diastolic) - mm Hg | 91 – 95 | 96 – 100 | > 100 | ER visit or hospitalization for malignant hypertension |
| Hypotension (systolic) – mm Hg | 85 – 89 | 80 – 84 | < 80 | ER visit or hospitalization for hypotensive shock |
| Respiratory Rate – breaths per minute | 17 – 20 | 21 – 25 | > 25 | Intubation |

* Participant should be at rest for all vital sign measurements.

** Oral temperature; no recent hot or cold beverages or smoking.

*** When resting heart rate is between 60 – 100 beats per minute. Use clinical judgment when characterizing bradycardia among some healthy participant populations, for example, conditioned athletes.

9.10. Appendix I Censoring Rules for Efficacy Endpoint Cases**Table 14: Censoring Rules for the Primary Efficacy Endpoint and Secondary Efficacy Endpoints Cases**

| Situation | Censoring Approach |
|---|---|
| Without Efficacy Endpoint Case | Censored at Day 181/Month 6 or at the end of the influenza season, whichever occurs later; or at the data cutoff date for interim analyses. |
| Early discontinuation or death unrelated to influenza | Censored at date of discontinuation/death |
| Early ILI up to 14 days after study vaccination | Censored at date of documented case |
| (Secondary endpoints only) Unknown or undetermined antigenic match or similarity status for an RT-PCR confirmed ILI due to missing data. | Censored at the ILI start date |
| Secondary endpoints including RT-PCR confirmed US CDC-defined ILI, culture-confirmed protocol-defined ILI, and culture-confirmed US CDC-defined ILI endpoints: In the case that no events satisfy the definition for the particular endpoint, but RT-PCR confirmed protocol-defined ILI occurred. | Censored at the first RT-PCR confirmed protocol-defined ILI start date (regardless of whether or not ≥ 14 days post-vaccination) |

9.11. Appendix J Definition of TEAE of Special Interest by SMQ**Table 15: TEAE of Special Interest by SMQ**

| TEAE of Special Interest | Type of MedDRA Query | Broad or Narrow Search | SMQ Search Criteria |
|---------------------------------|-----------------------------|-------------------------------|--|
| Hypersensitivity | SMQ | Broad/Narrow | Specified PT terms |
| Angioedema | SMQ | Broad/Narrow | Specified PT terms |
| Anaphylactic Reaction | SMQ | Broad/Narrow | Specified PT terms and algorithmic approach specified in Table 18. |
| Autoimmune Disorder | SMQ | Broad/Narrow | Specified PT terms |

Table 16: Algorithmic Approach for Anaphylactic Reaction

The following criteria will be used to determine anaphylactic reaction:

- Any term where Category = A
- Any term where Category = B (Upper Airway/Respiratory) and any term where Category = C (Angioedema/Urticaria/Pruritus/Flush) that occurred within 24 hours of each other.
- Any term where Category = D (Cardiovascular/Hypotension) and at least one of the following:
 - o Any term from Category = B (Upper Airway/Respiratory) that occurred within 24 hours of each other.
 - o Any term from Category = C (Angioedema/Urticaria/Pruritus/Flush) that occurred within 24 hours of each other.

| Anaphylactic Reaction | | |
|------------------------------|--------------|-----------------------------------|
| Category | Scope | PT Search Term |
| A | Narrow | Anaphylactic reaction |
| A | Narrow | Anaphylactic shock |
| A | Narrow | Anaphylactic transfusion reaction |
| A | Narrow | Anaphylactoid reaction |
| A | Narrow | Anaphylactoid shock |
| A | Narrow | Circulatory collapse |
| A | Narrow | Dialysis membrane reaction |
| A | Narrow | Kounis syndrome |
| A | Narrow | Procedural shock |
| A | Narrow | Shock |
| A | Narrow | Shock symptom |
| A | Narrow | Type I hypersensitivity |
| B | Broad | Asthma |
| B | Broad | Bronchial oedema |
| B | Broad | Bronchospasm |
| B | Broad | Cardio-respiratory distress |
| B | Broad | Chest discomfort |
| B | Broad | Choking |

| | | |
|---|-------|---|
| B | Broad | Choking sensation |
| B | Broad | Circumoral oedema |
| B | Broad | Cough |
| B | Broad | Cough variant asthma |
| B | Broad | Cyanosis |
| B | Broad | Dyspnoea |
| B | Broad | Hyperventilation |
| B | Broad | Irregular breathing |
| B | Broad | Laryngeal dyspnoea |
| B | Broad | Laryngeal oedema |
| B | Broad | Laryngospasm |
| B | Broad | Laryngotracheal oedema |
| B | Broad | Mouth swelling |
| B | Broad | Nasal obstruction |
| B | Broad | Oedema mouth |
| B | Broad | Oropharyngeal oedema |
| B | Broad | Oropharyngeal spasm |
| B | Broad | Oropharyngeal swelling |
| B | Broad | Pharyngeal oedema |
| B | Broad | Pharyngeal swelling |
| B | Broad | Respiratory arrest |
| B | Broad | Respiratory distress |
| B | Broad | Respiratory failure |
| B | Broad | Reversible airways obstruction |
| B | Broad | Sensation of foreign body |
| B | Broad | Sneezing |
| B | Broad | Stridor |
| B | Broad | Swollen tongue |
| B | Broad | Tachypnoea |
| B | Broad | Throat tightness |
| B | Broad | Tongue oedema |
| B | Broad | Tracheal obstruction |
| B | Broad | Tracheal oedema |
| B | Broad | Upper airway obstruction |
| B | Broad | Vaccine associated enhanced respiratory disease |
| B | Broad | Wheezing |

| | | |
|---|-------|------------------------------------|
| C | Broad | Allergic oedema |
| C | Broad | Angioedema |
| C | Broad | Circumoral swelling |
| C | Broad | Erythema |
| C | Broad | Eye oedema |
| C | Broad | Eye pruritus |
| C | Broad | Eye swelling |
| C | Broad | Eyelid oedema |
| C | Broad | Face oedema |
| C | Broad | Flushing |
| C | Broad | Injection site urticaria |
| C | Broad | Lip oedema |
| C | Broad | Lip swelling |
| C | Broad | Nodular rash |
| C | Broad | Ocular hyperaemia |
| C | Broad | Oedema |
| C | Broad | Oedema blister |
| C | Broad | Periorbital oedema |
| C | Broad | Periorbital swelling |
| C | Broad | Pruritus |
| C | Broad | Pruritus allergic |
| C | Broad | Rash |
| C | Broad | Rash erythematous |
| C | Broad | Rash pruritic |
| C | Broad | Skin swelling |
| C | Broad | Swelling |
| C | Broad | Swelling face |
| C | Broad | Swelling of eyelid |
| C | Broad | Urticaria |
| C | Broad | Urticaria papular |
| D | Broad | Blood pressure decreased |
| D | Broad | Blood pressure diastolic decreased |
| D | Broad | Blood pressure systolic decreased |
| D | Broad | Cardiac arrest |
| D | Broad | Cardio-respiratory arrest |
| D | Broad | Cardiovascular insufficiency |

Moderna TX, Inc.
mRNA-1010-P302

Statistical Analysis Plan, Version 2.0
Date Issued: 23FEB2023

| | | |
|---|-------|-----------------------------|
| D | Broad | Diastolic hypotension |
| D | Broad | Hypotension |
| D | Broad | Hypotensive crisis |
| D | Broad | Post procedural hypotension |

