The most commonly reported local solicited ARs after interim safety analysis in the mRNA-1010-P101 trial were pain at injection site, axillary swelling, or tenderness. Injection site erythema or swelling was less frequently reported. The most common solicited systemic reactions were headache, fatigue, myalgia, and chills. Fever, nausea and arthralgia were reported less frequently.

There have been very rare reports of myocarditis and pericarditis occurring after vaccination with COVID-19 mRNA vaccines. The majority of the cases have been reported in young males shortly after the second dose of the vaccine. These are typically mild cases and individuals tend to recover within a short time following standard treatment and rest. Investigators and study participants should be alert to the signs and symptoms of myocarditis and pericarditis ([Gargano et al, 2021](#)).

Enhanced influenza vaccines (eg, adjuvanted, high dose, or recombinant vaccines) are preferentially recommended and available to the elderly (~65 years of age and older) in some countries. These vaccines are more efficacious in preventing influenza illness compared to standard dose vaccines (eg, the comparator Fluarix[®]). Moreover, the efficacy of mRNA-1010 is unknown and will be evaluated in this study. Therefore, elderly participants should be made aware of any available alternative option to receive an enhanced influenza vaccine during the consenting process. Nonstudy influenza vaccines are not permitted in the study.

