6.7.2. Unsolicited Treatment-emergent Adverse Events

A TEAE is defined as any event that is not present before exposure to the study intervention or any event already present that worsens in intensity or frequency after exposure. Worsening of a pre-existing condition after vaccination will be reported as a new AE.

AEs will also be evaluated by the investigator for the coexistence of MAAEs and/or AESIs. A MAAE is an AE that leads to an unscheduled or scheduled visit to a healthcare practitioner. AESIs for this study are pre-defined in the protocol ([Table 12](#)) including thrombocytopenia, neurologic diseases, anaphylaxis, and myocarditis/pericarditis.

Unsolicited AEs will be collected from Day 1 up to 28 days after vaccination on the AE page and reactogenicity page of the eCRF. SAEs, MAAEs, AESIs, and AEs leading to discontinuation from study participation will be collected from Day 1 until the end of participation in the study. Analyses of unsolicited AEs will be provided for events occurring up to 28 days after vaccination unless otherwise specified.

Unsolicited AEs will be coded by PT and SOC using MedDRA and summarized by vaccination group.

All summary tables for unsolicited AEs will be presented by SOC and PT or by PT only for TEAEs with counts of participants included. SOC will be displayed in internationally agreed order. PTs will be displayed in descending order of frequency in the mRNA-1010 group and

then alphabetically within SOC. When summarizing the number and percentage of participants with an event, participants with multiple occurrences of the same AE or a continuing AE will be counted once. Only the maximum severity level will be presented in the severity summaries, and the strongest relationship level will be presented in the relationship summaries.

Unsolicited TEAEs occurring up to 28 days after IP injection and occurring throughout the study (up to Day 361/EoS) Will be summarized.

In addition, the number of participants with occurrences of selected TEAEs of clinical interest identified by standardized MedDRA queries (SMQ) will be summarized. SMQ will be summarized by PT, if applicable. Detailed descriptions of SMQ are presented in [Table 15](#) and [Table 16](#).

Percentages will be based upon the number of participants in the Safety Set within each treatment group.

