6.7.1.1. Overview of Unsolicited TEAEs

An overall summary of unsolicited TEAEs occurring up to 28 days after IP injection including the number and percentage of participants, along with the number of events, by vaccination group who experience the following will be presented:

- Any unsolicited TEAEs
- Any unsolicited treatment-related TEAEs
- Any serious TEAEs
- Any treatment-related serious TEAEs
- Any unsolicited severe TEAEs
- Any unsolicited treatment-related severe TEAEs
- Any unsolicited treatment-emergent MAAEs
- Any unsolicited treatment-related treatment-emergent MAAEs

- Any unsolicited treatment emergent AESIs
- Any unsolicited TEAEs leading to discontinuation from participation in the study
- Any unsolicited TEAEs that are fatal

In addition, separate listings containing individual participant AE data for unsolicited AEs, unsolicited serious AEs, unsolicited severe AEs, unsolicited MAAEs, unsolicited AESIs as assessed by investigator, unsolicited AEs leading to discontinuation from participation in the study, and unsolicited adverse events leading to death will be produced. A separate listing of deaths will also include the cause of death.

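### SAP Table 15 names a coded-term query for only one of the four AESI categories, leaving three with no named check on the investigator's flag

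*SAP*

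**What the plan says.** AESIs from Day 1 to Day 361/EoS are a primary safety endpoint (Protocol Section 3, Table 2; SAP Section 3.1.1). SAP Section 6.7.2 gives the categories as "including thrombocytopenia, neurologic diseases, anaphylaxis, and myocarditis/pericarditis". Protocol Table 11 (Appendix 4) and SAP Table 12 (Appendix G) define them. The neurologic category, "New onset of or worsening of the following neurologic diseases", covers Guillain-Barré syndrome, acute disseminated encephalomyelitis, Bell's palsy and seizures.

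AESI status is the investigator's call. SAP Section 6.7.2 has the investigator evaluate AEs for AESI status, and the listing in the SAP's overview of unsolicited TEAEs (numbered 6.7.1.1) is of "unsolicited AESIs as assessed by investigator". Protocol Appendix 4 asks investigators to report events in the categories.

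Separately, Section 6.7.2 says that participants with "selected TEAEs of clinical interest identified by standardized MedDRA queries (SMQ) will be summarized" and refers to Tables 15 and 16 for the details. Table 15 (Appendix J) is headed "Table 15: TEAE of Special Interest by SMQ" and has four rows: hypersensitivity, angioedema, anaphylactic reaction and autoimmune disorder. Table 16 sets out the terms and algorithm for anaphylactic reaction only.

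**The concern.** A search of coded terms is an independent check on a flag that depends on site recognition. The SAP already uses such a search and writes it out in full for anaphylaxis, but names none for the other three AESI categories.

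One of those three is the risk that the protocol singles out for this vaccine platform: "There have been very rare reports of myocarditis and pericarditis occurring after vaccination with COVID-19 mRNA vaccines". Another, thrombocytopenia, is defined by a platelet count threshold plus an open-ended list of diagnoses. The schedule of events has no routine haematology, so such findings will mostly reach the database from outside care, as recorded terms that a site may or may not recognise as AESIs.

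At stake is the completeness of a primary safety count by arm. If a qualifying event is recorded as an AE, MAAE or SAE but not flagged, the planned AESI table omits it, and no planned output brings such events together by category.

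**Working it through.** No power, alpha or sample-size figure is involved. The check compares the passages with one another.

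**Step 1. AESI categories against Table 15 rows.**

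| AESI category (Protocol Table 11, SAP Table 12) | Query of that name in SAP Table 15 | Terms written out |
|---|---|---|
| Thrombocytopenia | None | No |
| Listed neurologic diseases | None | No |
| Anaphylaxis | Anaphylactic reaction | Yes, Table 16 |
| Myocarditis/pericarditis | None | No |

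By name, 1 of 4 categories is covered and 4 − 1 = 3 are not. Of the four queries, 4 − 1 = 3 are not AESI categories. The row "Autoimmune Disorder | SMQ | Broad/Narrow | Specified PT terms" could reach some immune-mediated AESI terms, but the SAP does not list its preferred terms, so the overlap cannot be determined. Any hit would be reported under that query and not by AESI category.

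**Step 2. Routes to AESI status.** Both documents give one route, the investigator's assessment, and it applies to all four categories (Protocol Section 8.10.6 and Appendix 4; SAP Sections 6.7.2 and 6.7.1.1). The cardiac adjudication committee (Protocol Sections 8.10.6.2 and 8.11.2) classifies suspected cases put to it. A suspected case is an AESI whether or not it meets the CDC definition, and no term search is described for finding cases that were not suspected.

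**Step 3. Where a recorded but unflagged event goes.** Take a Bell's palsy with no AESI flag.

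- *Onset by Day 28:* it is in the unsolicited TEAE tables by SOC/PT and by PT (SAP 6.7.1.2 and 6.7.1.3), but not in the AESI rows.
- *Onset after Day 28, and serious, medically attended, fatal or leading to discontinuation:* it is in the corresponding SOC/PT table through Day 361/EoS (SAP 6.7.1.2), but not in the AESI table.
- *Onset after Day 28 and none of these:* it falls outside routine AE collection, so it may never be recorded. A term search cannot recover it.

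**Step 4. Can a reader rebuild the category count from those tables?** Only roughly. SAP Table 12 names six conditions under thrombocytopenia alone (immune thrombocytopenia, platelet production decreased, thrombocytopenia, thrombocytopenic purpura, thrombotic thrombocytopenic purpura, HELLP syndrome), and says the list is not exhaustive. Participants are counted once per preferred term, so adding the rows would count anyone with two terms twice.

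**Step 5. Cross-reference.** Table 15 describes the anaphylaxis row as "Specified PT terms and algorithmic approach specified in Table 18". The algorithm is in Table 16, which is where Section 6.7.2 points.

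**The case against.** The strongest reply is that the SMQ summary was never meant to police the AESI count. Section 6.7.2 introduces it as an addition covering selected events of clinical interest, and nowhere says that it defines, feeds or checks the AESIs. That stands, so there is no contradiction between Table 15 and Table 12. A reader might infer from the similar label in Table 15 that the SMQs define the AESIs, or that the missing queries are why three categories depend on the investigator. The documents do not support either inference: the flag governs anaphylaxis as well, and an unflagged anaphylaxis would also be absent from the AESI count.

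A second reply is that nothing recorded is lost. That also stands, as Step 3 shows. What the tables lack is grouping by category and comparison with the flag.

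A third is that capture is already protected. Safety-call scripts ask about AESIs (Protocol Section 8.9.3), investigators must obtain enough information on each AE to judge AESI status (8.9.10), monitors verify source data (11.1.2), suspected cardiac cases go to adjudication, and the DSMB sees unblinded safety data (11.1.11). These make under-flagging less likely. None is a systematic search of coded terms, and the adjudication committee does not cover platelet or neurologic events.

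Finally, a reader might take Appendix 4 to require that every qualifying event be counted in the analysis. It sets a reporting duty for investigators, and an investigator-assessed AESI table is consistent with that.

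**Conclusion.** The point holds as a gap in checking, and its remedy is a cheap improvement. Three of the four AESI categories have no named term-based check on the investigator's flag, and whether the autoimmune query partly fills the gap cannot be settled from the SAP.

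The number of AESIs that might go unflagged cannot be estimated, because neither document gives a flagging rate or expected event rates for the three uncovered categories. Nor do the documents give reason to expect under-flagging to differ between arms in an observer-blind trial, so a claim of bias in the comparison would go too far. No hypothesis test or decision rule uses the AESI count; Protocol Table 7 plans counts and percentages only.

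The conclusion assumes that the AESI tables are built from the investigator's assessment, the only basis either document gives, and that no charter or data-review plan outside these documents already contains such a search.

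**What to change.** Add three rows to SAP Table 15:

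- thrombocytopenia;
- Guillain-Barré syndrome, acute disseminated encephalomyelitis, Bell's palsy and seizures;
- myocarditis/pericarditis.

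Define each by SMQ or by a preferred-term list fixed before unblinding. SAP Section 4.5 allows a designated sponsor team to be unblinded after the interim analysis, so staff who remain blinded should set the lists and review the hits.

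Run the searches blinded on all recorded AEs through Day 361/EoS and query sites about unflagged hits before database lock. Report the term-identified counts by arm beside the investigator-assessed AESI counts, with a listing of hits that stay unflagged. The investigator-assessed AESI definition does not change.

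In the same edit, correct Table 15's pointer from Table 18 to Table 16, and state in Section 6.7.2 that the SMQ summary is separate from the AESI count.

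The cost is three term lists, one added table with its listing, and blinded review of some false-positive terms. The searches use data already collected; the only added site work is answering the queries.
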